6.7.3 Laboratory Data

Laboratory data will be summarized by treatment arm at each assessment time point. Values outside the normal ranges will be summarized by treatment arm. In addition, selected laboratory data will be summarized by treatment arm and NCI CTCAE v4.0 grade at each assessment time point.

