9.4.1 Safety

Please refer to the current CB-839 Investigator's Brochure for the most recent safety information for CB-839 monotherapy and CB-839 in combination regimens.

CB-839 Monotherapy

Treatment-related AEs for patients enrolled on Study CX-839-001 who received monotherapy with CB-839 on the BID fed regimen are presented in [Table 9.5-1](#). Of 88 safety-evaluable patients, 61 (69.3%) experienced AEs that were considered possibly or probably related to CB-839. The most frequent CB-839-related AEs were fatigue, gastrointestinal AEs (e.g., nausea, decreased appetite, and vomiting), liver function test (LFT) elevations (e.g., AST, ALT), and photophobia. These AEs were typically mild to moderate in intensity (Grade 1/2), reversible, and manageable without dose interruption or modification.

The most frequent Grade 3 AEs were elevations in LFTs, including AST, ALT, and alkaline phosphatase. Gamma-glutamyltransferase elevations were also noted but are of unclear clinical significance. The frequency of Grade 3 elevations in LFTs was limited, with 2 of 88 patients experiencing a treatment-related Grade 3 AST or ALT elevation. One Grade 3 AE of anemia was also considered to be possibly related to CB-839 (not shown). There have been no reported Grade 4 or Grade 5 treatment-related adverse events.

Table 9.5-1: CB-839 Related Adverse Events in $\geq 5\%$ of Patients Treated with Monotherapy CB-839 on the BID Schedule on Study CX-839-001

BID fed - Monotherapy (N=88)		
MedDRA Preferred Term	Number (%) of patients	
	All Grades	Grade 3
Patients with Any CB-839-Related AE	61 (69.3)	3 (3.4)
Fatigue	22 (25.0)	0
Nausea	20 (22.7)	0
Alanine aminotransferase increased	13 (14.8)	2 (2.3)
Photophobia	12 (13.6)	0
Aspartate aminotransferase increased	10 (11.4)	1 (1.1)
Decreased appetite	7 (8.0)	0
Gamma-glutamyltransferase increased	7 (8.0)	2 (2.3)
Blood alkaline phosphatase increased	6 (6.8)	1 (1.1)

Vomiting	5 (5.7)	0
23July2017 data cut		

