10.6.6 Electrocardiograms

Patients should rest in the supine or semi-recumbent position for at least 5 min before the 12-lead ECG recording is started. ECG recordings must be performed using a standard, high-quality, high-fidelity electrocardiograph machine equipped with computer-based interval measurements.

When performed, the ECG must be reviewed by a qualified physician (or qualified physician's assistant or nurse practitioner), and any clinically important finding should be recorded on the appropriate electronic case report form (eCRF). ECG results will include heart rate, R-R interval, PR interval, QRS interval, QT interval, and QTc interval.

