11.1.4.2 Hepatobiliary Disorders

Elevations of ALT, AST, and bilirubin have been observed during treatment with cabozantinib. It is recommended that patients with elevation of ALT, AST, and/or bilirubin have more frequent laboratory monitoring of these parameters. If possible, hepatotoxic concomitant medications should be discontinued in patients who develop increased values of ALT, AST, or bilirubin.

Patients on this study may enter with increased ALT/AST serum levels up to $3 \times \text{ULN}$. Dose reductions of study treatment should be considered in any patient who develops drug-related Grade 2 elevated ALT, AST, or bilirubin lasting longer than 1 week. A patient who develops Grade ≥ 3 elevated ALT, AST, or bilirubin should have study treatment held and restarted at a reduced dose (see [Table 11.1-3](#)) after ALT, AST, and bilirubin levels resolve to at least Grade ≤ 1 or baseline. In patients with recurrence of drug-related Grade ≥ 3 elevated ALT, AST, or bilirubin at the lowest dose level, study treatment should be discontinued. In patients who develop ALT/AST elevations $> 3 \times \text{ULN}$ in combination with a bilirubin elevation $> 2 \times \text{ULN}$ without reasonable other explanation, drug-induced liver injury should be suspected and study treatment interrupted. Reinstitution of study treatment after recovery of ALT, AST, and bilirubin to Grade 1 or baseline level must be discussed and approved with the Sponsor.

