AE = adverse event, CT = computed tomography, ECG = electrocardiogram, MRI = magnetic resonance imaging, QoL = quality of life.

- ¹ An IRB/EC approved Informed Consent Form (ICF) must be signed and dated ≤42 days prior to randomization. Assessments must be completed within 28 days prior to randomization, unless otherwise indicated. Results of screening assessments must be reviewed before randomization to confirm that the patient meets all eligibility criteria.
- ² Starting with Cycle 13, clinic visits and assessments will be completed at least every 12 weeks. More frequent visits should be completed if clinically indicated.
- ³ Assessments on C1D1 should be completed prior to first dose of study treatment; assessments completed during Screening within 3 days of C1D1 are not required to be repeated on C1D1.
- ⁴ Patients will be followed for safety for at least 28 days after the last dose of all study treatments (CB-839/placebo and cabozantinib) or until initiation of a new anticancer therapy, if earlier.
- ⁵ Complete physical exam is required at Screening and at the End of Treatment Visit. A symptom-directed physical exam can be done on all other visits. At Screening patient should be questioned about any symptoms of potential CNS disease (e.g., unusual headaches, falls, changes in balance or coordination, focal weakness, dizziness, seizure, new confusion or memory loss). A positive CNS review of systems should be followed by baseline CNS imaging if not already done.
- ⁶ Patients should be sitting for at least 3 min prior to collection of vital signs (temperature, pulse, respiratory rate and resting systolic and diastolic blood pressure.)
- ⁷ An ECG assessment will be completed at Screening, on Day 1 of Cycles 2-4 and every 3 cycles thereafter.
- ⁸ Post-Screening urinalysis only requires monitoring for proteinuria (dipstick acceptable and if positive will be followed by UPCR).
- ⁹ Coagulation assessment will be completed at Screening and as clinically indicated during the study.
- ¹⁰ Thyroid function tests include TSH and free-T4 at Screening, then TSH with free-T4 only if TSH is out normal range. Additional testing may be performed as clinically indicated.

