4.1.3 Safety Endpoints

The safety endpoints are the following:

- Type, incidence, severity, seriousness, and study drug-relatedness of adverse events graded according to the National Cancer Institute Common Terminology Criteria for Adverse Events, Version 4.03 (NCI CTCAE v4.03)
- Changes in vital signs, ECGs, physical findings, and clinical laboratory test results and following study treatment administration

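### The SAP's safety section has no worst post-baseline laboratory grade or shift table, no by-arm count of joint ALT/AST and bilirubin elevation, and no analysis of its own ECG endpoint

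*SAP*

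**What the plan says.** SAP 6.7.3 plans three laboratory outputs by arm:

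- a summary of values at each time point;
- an out-of-range summary: "Values outside the normal ranges will be summarized by treatment arm";
- a graded summary: "selected laboratory data will be summarized by treatment arm and NCI CTCAE v4.0 grade at each assessment time point". The selected tests are not named.

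SAP 4.1.3 includes among the safety endpoints "Changes in vital signs, ECGs, physical findings, and clinical laboratory test results". SAP 6.7 then has subsections for exposure, adverse events, laboratory data and vital signs only.

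The protocol collects ECGs repeatedly. Attachment 1 says "An ECG assessment will be completed at Screening, on Day 1 of Cycles 2-4 and every 3 cycles thereafter", and section 10.6.6 says "ECG results will include heart rate, R-R interval, PR interval, QRS interval, QT interval, and QTc interval".

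On the liver, protocol 9.4.1 reports of CB-839 monotherapy that "The most frequent Grade 3 AEs were elevations in LFTs, including AST, ALT, and alkaline phosphatase". Protocol 11.1.4.2 says that when ALT/AST exceeds 3 x ULN in combination with bilirubin above 2 x ULN, and no other reasonable cause is found, "drug-induced liver injury should be suspected and study treatment interrupted".

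**The concern.** The protocol's safety objective is a comparison of the two arms, and liver enzyme elevation is a known effect of CB-839 that is also seen with cabozantinib. A table of grades at each time point answers how many patients were at a given grade on that occasion. It does not answer how many patients ever reached that grade, or how many worsened from where they started. Those per-patient questions are the ones a comparison of tolerability needs.

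Two further items have no output at all. The protocol defines a combined liver criterion that triggers action, yet no table shows how often each arm met it. ECG change is a named endpoint with repeated QTc measurements, yet no summary is planned. The study could be reported exactly as the SAP specifies without a by-arm statement on either.

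**Working it through.** There is no stated figure to reproduce, so the check is a side-by-side reading of SAP 4.1.3 and 6.7 with protocol 10.6.6, 10.6.7, 11.1.3.2, 11.1.4.2, 14.7 and 15.1.

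**1. ECG endpoint against planned analyses.** SAP section 3 says the SAP takes precedence over the protocol on analyses and endpoints, so the ECG entry in 4.1.3 is current. Of the items in that entry, vital signs have 6.7.4 and laboratory results have 6.7.3. ECGs have no analysis, and neither do physical findings. QTc matters to this protocol: exclusion criterion 1f uses a 500 msec threshold and urges caution with cabozantinib in patients with a history of QT prolongation.

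**2. Graded laboratory data.**

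- The grade summary is tied to time points. Scheduled visits are about 4 weeks apart to Cycle 12 and every 3 cycles from Cycle 13.
- Protocol 11.1.4.2 recommends more frequent liver tests once values rise, and 10.6.7 has laboratory results entered in EDC. The SAP does not say how unscheduled values enter the tables.
- Protocol 11.1.4.2 lets patients enter with ALT/AST up to 3 x ULN. A grade at a visit, without the baseline grade beside it, does not separate elevation present at entry from elevation on treatment.
- The out-of-range summary has no visit limit, but it states no grade or multiple of ULN, so it does not separate a mild from a marked rise.

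**3. Joint criterion.** Neither SAP 6.7 nor protocol 14.7 tabulates it. Adverse event tables are built on MedDRA preferred terms, and ALT and AST are separate terms even in the protocol's own Tables 9.5-1 and 9.5-2. Counts by term cannot show that a transaminase and bilirubin rose together in one patient.

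**4. What the adverse event tables already cover.** Protocol 11.1.3.2 interrupts both drugs for Grade 3 or higher ALT, AST or bilirubin and for suspected drug-induced liver injury. Protocol 15.1 makes a laboratory result an adverse event if it comes with symptoms, changes study medication or changes concomitant therapy. SAP 6.7.2 counts each patient once per event at maximum grade, by arm, with separate summaries of Grade 3 or higher events and of events leading to interruption or discontinuation. Severe liver elevations should therefore be compared between arms whatever the visit timing.

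**5. What remains.** Below Grade 3, interruption is not mandatory; for drug-related Grade 2 lasting over a week, dose reduction is only to be considered. Entry as an adverse event then depends on the 15.1 triggers and the investigator's judgement. Much of the Phase 1 liver signal was in this range:

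| Source | Term | All grades | Grade 3 or higher | Below Grade 3 |
|---|---|---|---|---|
| Table 9.5-1, monotherapy, N = 88 | ALT increased | 13 | 2 | 13 - 2 = 11 |
| Table 9.5-1, monotherapy, N = 88 | AST increased | 10 | 1 | 10 - 1 = 9 |
| Table 9.5-2, with cabozantinib, N = 13 | ALT increased | 6 | 0 | 6 - 0 = 6 |
| Table 9.5-2, with cabozantinib, N = 13 | AST increased | 5 | 0 | 5 - 0 = 5 |

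These were all reported as adverse events. The table shows the range in which reporting is discretionary, not how many cases would be missed in this trial.

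**The case against.** The strongest reply is the route in step 4: the severe cases are already compared by arm at maximum grade. That stands. A reader might infer from the time-point wording that liver toxicity is graded only visit by visit and that severe peaks between visits are never compared. The documents do not support that reading.

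Nor do they exclude unscheduled draws. SAP 6.7.3 speaks of assessment time points, whereas 6.7.4 ties vital signs explicitly to scheduled collection. The SAP is silent on the matter, which is a missing rule and not a stated exclusion.

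The adverse event net is also wider than symptoms and treatment changes. Protocol 11.1.4.2 asks that hepatotoxic concomitant drugs be stopped where possible when liver values rise, which meets the third trigger in 15.1, and 10.6.7 asks for clinically significant results to be entered as medical history or adverse events. Many lower-grade elevations would qualify. This narrows the gap but leaves capture dependent on reporting, while the laboratory values themselves are in the database.

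On importance, Grade 3 AST or ALT elevation was limited in monotherapy (2 of 88 patients) and absent in the 13 combination patients. The IDMC sees unblinded safety data, all data will be listed, and clinically important ECG findings go on the eCRF. These points reduce the urgency. Listings and IDMC review are still not a by-arm summary in the study report, and none of them supplies the missing ECG analysis.

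**Conclusion.** The point holds in a limited form. The SAP lacks a worst post-baseline grade or shift table from laboratory values, a rule for unscheduled draws, a by-arm count of joint ALT/AST and bilirubin elevation, and any analysis of the ECG change it names as an endpoint. The comparison that is lost concerns elevations not reported as adverse events, joint elevation within a patient, and QTc.

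No size can be attached. The liver frequencies in the documents are adverse event frequencies, which SAP 6.7.2 would show without dilution, and no duration of elevation is given. The conclusion that severe elevations are covered assumes that investigators follow the interruption rule and report the resulting events. The point concerns descriptive safety reporting only; the PFS and OS analyses, sample size and alpha are unaffected.

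**What to change.** Amend SAP 6.7 before unblinding:

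- **6.7.3, grades.** Name the selected tests. Add, by arm, the shift from baseline grade (as defined in SAP 6.2) to worst post-baseline CTCAE grade, using scheduled and unscheduled values through the end of safety follow-up. The time-point tables can stay.
- **6.7.3, liver.** Add a by-arm count and a listing of patients with ALT or AST above 3 x ULN together with bilirubin above 2 x ULN. Label this as the laboratory part of the 11.1.4.2 criterion. The requirement that no other reasonable explanation exists cannot be read from laboratory values and needs case review.
- **New ECG subsection.** By arm, give worst post-baseline QTc in categories, including above 500 msec (the threshold already in exclusion criterion 1f), and maximum change from baseline.
- **Physical findings.** State how this item of the 4.1.3 endpoint will be reported, or remove it.

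The cost is a few extra tables and one listing from data already in EDC, plus the case review. No new assessments are needed and no clinical rule changes.

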6.7.4 Vital Signs

Changes in selected vital signs will be summarized by treatment arm and by change over time, which includes change from baseline at each visit where parameters are scheduled to be collected. Baseline is defined as the measurement obtained on Cycle 1, Day 1 before the first dose of study drug is administered.

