10.2 Randomization

Patients eligible after completing all screening evaluations will be randomly assigned by an interactive response technology (IRT) system in a 1:1 ratio to receive CB-Cabo or Pbo-Cabo.

Randomization will be stratified by the following factors:

- Prior treatment with PD-1/PD-L1 inhibitor therapy: Yes vs. No
- IMDC Prognostic Risk Group: favorable vs. intermediate vs. poor ([Attachment 3](#))

Randomization should occur as close as possible to the planned start of treatment (i.e., within 24 hr if practicable but no more than 3 days). Patients are defined as enrolled in the study if randomized.

Crossover between treatment arms will not be allowed.

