10.6.3 Vital Signs

Vital signs (blood pressure, respiratory rate, pulse rate, and temperature) will be obtained in the sitting position. All patients should be sitting for at least 3 min prior to obtaining vital signs.

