11.1.4.6 Hypertension

Hypertension is a common class effect of drugs that inhibit VEGF pathways and has been reported in patients treated with cabozantinib.

Blood pressure should be monitored in a constant position at each visit (either sitting or supine). Treatment guidelines for hypertension deemed related to cabozantinib are presented in [Table 11.1-5](#). In general, patients with known hypertension should be optimally managed prior to study entry. Decisions to decrease or hold the dose of study treatment must be based on blood pressure

readings taken by a medical professional and must be confirmed with a second measurement at least 5 minutes following the first measurement. Other than for hypertension requiring immediate therapy, the presence of new or worsened hypertension should be confirmed at a second visit before taking therapeutic action. It is recommended that this second visit occurs within 1 week.

Table 11.1-5: Management of Treatment-emergent Hypertension

Criteria for Dose Modification	Action To Be Taken

> 150 to <160 mm Hg (systolic) OR > 100 to <110 mm Hg (diastolic)
	
 • Optimize antihypertensive treatment by adding new or additional antihypertensive medications and/or increase dose of existing medications. • Reduce cabozantinib treatment by one dose level if optimal antihypertensive therapy (usually to include 3 agents) does not result in BP < 150 mm Hg systolic or < 100 mm Hg diastolic. • If patient is symptomatic interrupt study treatment.

≥ 160 mm Hg (systolic) OR ≥ 110 mm Hg (diastolic)
	
 • Reduce cabozantinib treatment by one dose level and add new or additional antihypertensive medications and/or increase dose of existing medications and monitor patient closely for hypotension. If optimized antihypertensive therapy (usually to include 3 agents) does not result in BP < 150 mm Hg systolic or < 100 mm Hg diastolic, cabozantinib treatment should be dose reduced further or interrupted. • Interrupt cabozantinib treatment if upper limits of BP (≥ 160 mm Hg systolic or ≥ 110 mm Hg diastolic) are sustained and not adequately manageable or if BP is > 180 mm Hg systolic or > 120 mm Hg diastolic or if patient is symptomatic. • Restart cabozantinib treatment at the most tolerable dose and re-escalate cabozantinib dose only if BP falls to and is sustained at < 140 mm Hg systolic and < 90 mm Hg diastolic.

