6.2 General Statistical Methods

Baseline values are defined as the last available data obtained prior to the patient receiving the first dose of any study treatments on Cycle 1 Day 1 visits unless otherwise noted. Descriptive statistics (mean, median, SD, range) will be presented for continuous variables, and frequencies and percentages will be presented for categorical variables.

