6.8 Missing Data

See [Section 6.5](#) for methods for handling missing data for primary and secondary efficacy endpoints. Missing data will not be imputed for safety analyses except for the purpose of identification of TEAEs and prior or concomitant medications with missing start or end date. Imputation rules for the partial or missing dates will be pre-specified in a separate document. All available data will be presented on the data listings as collected (no imputation).

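### SAP 6.7.4 ties the vital-sign baseline to a Cycle 1 Day 1 reading that Attachment 1 does not always require, so a compliant patient could lack a baseline if the rule is applied literally

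*SAP*

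**What the plan says.** SAP 6.7.4 plans summaries of selected vital signs by arm, including change from baseline at each visit where they are scheduled. It gives its own definition: "Baseline is defined as the measurement obtained on Cycle 1, Day 1 before the first dose of study drug is administered".

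SAP 6.2 gives the general definition: "Baseline values are defined as the last available data obtained prior to the patient receiving the first dose of any study treatments". The same sentence goes on to say that it yields where something else is noted.

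Protocol Attachment 1 schedules vital signs at Screening, on C1D1 and at later visits. The C1D1 cell carries footnote 3, under which "assessments completed during Screening within 3 days of C1D1 are not required to be repeated on C1D1".

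Protocol 10.2 sets the gap between randomization and the planned start of treatment at "within 24 hr if practicable but no more than 3 days".

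SAP 4.1.3 names among the safety endpoints "Changes in vital signs, ECGs, physical findings, and clinical laboratory test results".

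**The concern.** The protocol allows a recent Screening reading to take the place of the C1D1 reading. The vital-sign section of the SAP does not recognise that substitution. A patient whose site relied on the waiver has done nothing wrong and has an observed pre-dose value at most 3 days old, yet has no reading that meets the 6.7.4 definition. Without a baseline, none of that patient's later vital signs can enter a change-from-baseline summary.

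What is at stake is modest: some usable data for a named safety endpoint, and agreement between the SAP and the visit schedule. The SAP would also treat similar data differently. Serum chemistry and hematology carry the same footnote on C1D1, and SAP 6.7.3 sets no laboratory baseline of its own, so SAP 6.2 governs there. A patient could then have a laboratory baseline from Screening but no vital-sign baseline from the same day.

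**Working it through.** The plan gives no figure to reproduce. The check sets the texts side by side.

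1. **Is the C1D1 reading always required?** No. In Attachment 1 the C1D1 vital-signs cell is marked with footnote 3, which waives the repeat when the Screening assessment was within 3 days.

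2. **Can the waiver be met in practice?** Attachment 1 (footnote 1) requires Screening results to be reviewed before randomization, so Screening vital signs come before it. If randomization falls k days before C1D1, with k from 0 to 3, the days before randomization in which a Screening reading still qualifies are 3 − k:
   - k = 0: 3 − 0 = 3 days
   - k = 1 (about the preferred 24 hours): 3 − 1 = 2 days
   - k = 3 (the maximum): 3 − 3 = 0, so only a reading on the day of randomization qualifies

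   The window is narrow but open.

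3. **Which SAP rule governs?** SAP 6.2 would take the Screening value as the last one before first dose. It applies only where nothing else is noted, and 6.7.4 gives a different definition for vital signs. Read literally, 6.7.4 prevails.

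4. **Does the missing-data section change this?** SAP 6.8 says: "Missing data will not be imputed for safety analyses except for the purpose of identification of TEAEs and prior or concomitant medications" (the exception concerns missing start or end dates). That section does not create a baseline. Nor does it forbid one: a Screening reading is observed, so using it is not imputation. The gap comes from 6.7.4 alone.

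5. **How many patients?** The documents give no rate of waiver use. The possible range runs from none to every treated patient, with 416 planned for randomization, and nothing in the documents narrows it. Under the SAP 6.2 rule the loss from this cause is 0 whatever the rate.

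6. **Could the loss differ by arm?** The decision not to repeat vital signs is made before the first dose in a double-blind, placebo-controlled trial, under the same schedule in both arms. No mechanism for a difference is apparent.

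**The case against.** The strongest reply is that 6.7.4 only restates the general rule for the usual case, in which vital signs are taken on C1D1 before dosing. It does not say that no other value may be used, and it does not say that patients without a C1D1 reading are left out. A programmer might well fall back on SAP 6.2. This stands in part: exclusion is an inference from the wording and is not stated. But the sentence names a day, and the general rule defers to specific ones, so the fallback is not what the text directs.

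A second reply is that the loss may be close to zero. The waiver is optional, and sites may take vital signs on C1D1 anyway. Before randomization, results have to be reviewed and a medical monitor has to approve from a checklist (Protocol 10.1), which makes the 3-day window tight. This stands in full.

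A third reply is that a same-day baseline has some merit, because each patient who has one is measured on the day of first dose. That is fair, but the protocol has already accepted a reading up to 3 days old as a substitute.

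A reader might infer more than the documents support:

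- **That the affected patients leave the safety analysis.** They do not. SAP 6.1 keeps every treated patient in the Safety population, the adverse event tables do not depend on this baseline, and SAP 6.8 keeps all available data in the listings.
- **That SAP 6.8 forbids use of the Screening value.** It restricts imputation, and this value is observed.
- **That a particular share of patients or loss of precision can be stated.** No document gives a basis for one.

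**Conclusion.** The mismatch between SAP 6.7.4 and Attachment 1 is real and rests on current text in both documents. If 6.7.4 is applied as written, a compliant patient who uses the waiver has no vital-sign baseline and no change value, although a valid pre-dose reading exists and SAP 6.2 would accept it.

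The point is minor. Its reach is the descriptive vital-sign change tables, for which 6.7.4 plans no test or decision threshold. No bias between arms is expected, and neither the primary nor the secondary efficacy analyses are affected. The wording conflict is certain. The number of patients affected is unknown and may be nil. The conclusion assumes a literal reading of 6.7.4 and at least some use of the waiver.

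**What to change.** Delete the baseline sentence in SAP 6.7.4 so that SAP 6.2 governs, or replace it with the 6.2 rule written out: the last available vital-sign value before the first dose of any study treatment, including a Screening value that Attachment 1 footnote 3 allows to stand. Writing it out is slightly safer, because it leaves no doubt that a Screening reading counts.

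The cost is one sentence and no new data collection. There is one small downside. If a C1D1 reading is simply missed, with no qualifying Screening value, the 6.2 rule can reach back to an older one: Screening may be up to 28 days before randomization and C1D1 up to 3 days after it, so up to 28 + 3 = 31 days before first dose. If that is unwelcome, accept the C1D1 pre-dose value or, failing that, the last Screening value within 3 days of C1D1. That version matches the waiver and admits nothing older.
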